Abbreviation	Full Term
ADA	anti-drug antibody
AE	adverse event
ALP	alkaline phosphatase
ALT	alanine aminotransferase
aPTT/APTT	activated partial thromboplastin time
AST	aspartate aminotransferase
AUC	area under the drug concentration-time curve
BMI	body mass index
BUN	blood urea nitrogen
C5	complement component 5
cm	centimeter
C _{max}	maximum plasma concentration
CPK	creatine phosphokinase
CRP	C-reactive protein
CSR	clinical study report
CTCAE	Common Terminology Criteria for Adverse Events
ECG	electrocardiogram
eCRF	electronic case report form
ELISA	enzyme-linked immunosorbent assay
EQ-5D	EuroQol 5D questionnaire

EORTC-QLQ-C30	European Organization for Research and Treatment of Cancer-Quality of Life Questionnaire
FACIT-F	Functional Assessment of Chronic Illness Therapy-Fatigue Scale
GGT	gamma-glutamyl transferase
HR	heart rate
ICF	informed consent form
ICH	International Conference on Harmonization
INR	international normalized ratio
ISR	injection site reaction
kg	kilogram
LDH	lactate dehydrogenase
MAVE	major adverse vascular event
MCH	mean corpuscular hemoglobin
MCHC	mean corpuscular hemoglobin concentration
MCV	mean corpuscular volume
MedDRA	Medical Dictionary for Regulatory Activities
mg	milligram
NCI	National Cancer Institute
PD	pharmacodynamics
PK	pharmacokinetics
PNH	paroxysmal nocturnal hemoglobinuria
PT	prothrombin time
PT	Preferred Term

PTT	partial thromboplastin time
QOL	quality of life
RBC	red blood cell
SAE	serious adverse event
SAP	statistical analysis plan
SOC	system organ class
sRBC	sheep red blood cell
TEAE	treatment-emergent adverse event
t_{max}	time to corresponding C_{max}
ULN	upper limit of normal
VAS	visual analogue scale
WBC	white blood cell

1 INTRODUCTION

Study RA101495-01.203 is a multicenter, open-label, uncontrolled study to evaluate the safety, tolerability, efficacy, pharmacokinetics and pharmacodynamics of RA101495 in subjects with PNH who have an inadequate response to eculizumab treatment for PND.

The planned enrollment is approximately 6-8 subjects.

This Statistical Analysis Plan (SAP) describes data-handling and statistical procedures to be used for the analysis and reporting of efficacy and safety data collected under Study RA101495-01.203 (version 1.1 20 October 2016) and presented in the clinical study report (CSR). They are based on those presented in Section 13 of the study protocol. Any post-hoc or exploratory analyses not specified in this SAP will be identified as such when they are presented in the CSR. This SAP has been developed and finalized prior to locking the clinical database.

The SAP was written in accordance with the recommendations outlined in the International Conference on Harmonisation (ICH) E9 Guideline entitled “Guidance for Industry: Statistical Principles for Clinical Trials” and the most recent ICH-E3 Guideline, entitled “Guidance for Industry: Structure and Content of Clinical Study Reports.”

2 STUDY SUMMARY

2.1 STUDY OBJECTIVES

The objectives of the study are

- To assess the safety and tolerability of RA101495 in subjects with PNH
- To assess preliminary efficacy of RA101495 in subjects with PNH
- To assess the pharmacokinetics (PK) and pharmacodynamics (PD) of RA101495 in subjects with PNH.

2.2 STUDY DESIGN

Study RA101495-01.203 is a multicenter, open-label, uncontrolled study to evaluate the safety, tolerability, efficacy, pharmacokinetics and pharmacodynamics of RA101495 in subjects with PNH who have an inadequate response to eculizumab treatment for PND.

The study includes an 8-week screening period and a 12-week Treatment Period. During the Treatment Period, subjects will return to the clinic weekly for the first 4 weeks followed by visits every 2 weeks to evaluate safety, tolerability, efficacy, PK and PD. Additional assessments will include immunogenicity, Quality of Life (QOL)

questionnaires, biomarker samples, and optional pharmacogenomics. Safety assessments include physical exam, vital signs, electrocardiogram (ECG), clinical laboratory tests, and adverse events (AEs).

At the conclusion of the Treatment Period subjects who complete the study and are demonstrating benefit will have the option to enroll in an extension study to continue receiving treatment with RA101495. Alternatively, they may opt to receive standard-of-care treatment off study, after consultation with their treating physician. If the subject withdraws early from the RA101495-01.203 study for any reason, he/she will not be eligible for the extension study.

All subjects will receive a loading dose of 0.3 mg/kg to be administered subcutaneously (SC) at the Day 1 Visit. Following in-clinic education and training, all subjects will self-inject daily SC doses of 0.1 mg/kg of RA101495 for 12 weeks. Except for Day 1, on study clinic days, the dose should be administered after the PK and PD collection has been completed.

After at least 2 weeks of treatment with RA101495 at 0.1 mg/kg daily, if a subject has not achieved an adequate response (defined as a lactate dehydrogenase [LDH] $<1.5 \times$ ULN), and following evaluation of safety and tolerability data by the investigator and the medical monitor, the dose should be escalated to 0.3 mg/kg daily.

2.2.1 Number of Patients

The planned enrollment is approximately 6-8 subjects.

2.2.2 Randomization and Blinding Procedures

This is an open-label single-arm uncontrolled study.

2.2.3 Safety Assessments

Safety assessments will include evaluation of AEs and SAEs (including major adverse vascular event (MAVE criteria), clinical laboratory tests, ECGs, vital signs, and physical examinations. Safety evaluations will also include a determination of anti-drug antibodies (ADA).

2.2.3.1 Physical Examination

Physical examinations will include the following assessments:

- General inspection
- Weight (kg) and height (height in cm to be collected at screening visit only)
- Examination of the injection site and draining nodes
- Head/ears/eyes/nose/throat examination
- Mucosal examination for icterus

- Cardiac examination
- Auscultation of lungs
- Abdominal examination (liver, spleen, and lower abdomen)
- Assessment for neurological deficits
- Musculoskeletal assessment

Any abnormalities found will be recorded in the eCRF.

2.2.3.2 Vital Signs

Vital signs (heart rate, body temperature, and blood pressure) will be measured in the sitting position after resting for at least 5 minutes.

2.2.3.3 Electrocardiogram

ECGs will be assessed as normal or abnormal by the investigator; any abnormal findings will be described in the eCRF and the investigator will assess clinical significance.

2.2.3.4 *Neisseria meningitidis* Testing

All subjects must have a negative result for *Neisseria meningitidis* colonization via a throat swab prior to study entry.

2.2.3.5 Adverse Event Recording

An AE is any untoward medical occurrence in a subject administered a pharmaceutical product and which does not necessarily have a causal relationship with this treatment. An AE can therefore be any unfavorable and unintended sign (including a clinically significant abnormal laboratory finding, for example), symptom, or disease temporally associated with the use of a medicinal product, whether or not considered related to the medicinal product.

The following are not considered to be AEs despite requiring hospitalization:

- Pre-existing conditions that, in the opinion of the investigator, did not worsen or progress during study participation
- Routinely scheduled procedures or treatment
- Elective procedures that had been scheduled prior to study participation (i.e. signing of the informed consent form (ICF))

A Serious adverse event (SAE) is any untoward medical occurrence that:

- results in death
- is life-threatening (note that this refers to an event in which the subject was at risk of death at the time of the event; it does not refer to an event that hypothetically might have caused death if it were more severe)
- requires hospitalization or prolongation of existing hospitalization
- results in persistent or significant disability/incapacity
- results in a congenital anomaly/birth defect

An SAE may also be any other important medical event that may not be immediately life-threatening or result in death or hospitalization, but may jeopardize the subject or require intervention to prevent one of the other outcomes listed in the definition above. Examples of such events include intensive treatment in an emergency room or at home for bronchospasm, hyperkalemia, or convulsions that do not result in a formal hospitalization.

Elective hospitalizations scheduled prior to study participation (i.e. signing of the ICF) should not be reported as SAEs.

2.2.3.6 Blood Chemistry and Hematology

Clinical chemistry and hematology analytes to be collected are identified in Table 1 and should be performed as specified in the Time and Events (Table 2).

Table 1: Clinical Chemistry, Hematology, and Coagulation Analytes

Clinical Chemistry	Hematology
alanine aminotransferase (ALT)	free hemoglobin
albumin	haptoglobin
alkaline phosphatase (ALP)	hematocrit
amylase	hemoglobin
aspartate aminotransferase (AST)	mean corpuscular hemoglobin (MCH)
bicarbonate	mean corpuscular hemoglobin concentration (MCHC)
bile acids	mean corpuscular volume (MCV)
bilirubin (total, direct, and indirect)	platelet count
blood urea nitrogen (BUN)	RBC count
calcium	reticulocyte count
chloride	white blood cell (WBC) count and differential (%)
creatinine	
gamma-glutamyl transferase (GGT)	Coagulation
glucose	international normalized ratio (INR)/prothrombin time (PT)
lactate dehydrogenase (LDH)	fibrinogen
lipase	fibrinogen
potassium	
sodium	Other
total protein	C-reactive protein (CRP)
uric acid	creatine phosphokinase (CPK)

2.2.3.7 Urinalysis

A urinalysis will be performed to measure pH, specific gravity, protein (qualitative), glucose (qualitative), ketones (qualitative), bilirubin (qualitative), urobilinogen, occult blood, hemoglobin, and cells. A microscopic examination will be performed, if necessary. Hemoglobinuria will be assessed using a urine colorimetric scoring system.

2.2.3.8 Pregnancy Test

A serum pregnancy test for human chorionic gonadotropin will be performed on female subjects of childbearing potential at Screening.

A urine dipstick pregnancy test (human chorionic gonadotropin) will be performed on female subjects of childbearing potential at Day 1 pre-dose and Day 29, Day 57, and Day 84 (End of Study).

2.2.3.9 PNH Clone

Blood sample for measurement of PNH clone size will be collected at Screening and Day 29, Day 57, and Day 84 (or End-of-Study Visit). PNH clone size will be determined by peripheral blood flow cytometry analysis (RBCs and granulocytes).

2.2.3.10 Immunogenicity

Blood samples for ADAs will be collected prior to dosing on Day 1 and on Day 29, Day 57, and Day 84 (or at the End-of-Study Visit) in all enrolled subjects. Samples will be sent to a central laboratory to determine the presence or absence of antibodies against RA101495 using a validated assay.

Detailed instructions regarding sample collection, processing, and shipping will be provided in a separate laboratory manual.

2.2.4 Efficacy Assessments

Efficacy assessments include the measurement of serum LDH levels as a measure of intravascular hemolysis. Additional assessments will include laboratory assessments of total bilirubin, total hemoglobin, free hemoglobin, haptoglobin, reticulocytes, and hemoglobinuria.

2.2.5 Exploratory Assessments

Exploratory endpoints include:

- Changes from baseline in QOL questionnaires

- European Organization for Research and Treatment of Cancer-Quality of Life Questionnaire (EORTC QLQ-C30)
- Functional Assessment of Chronic Illness Therapy-Fatigue Scale (FACIT-Fatigue)
- EuroQol 5D (EQ-5D)
- Treatment satisfaction questionnaire

2.2.6 Pharmacodynamic Assessments

The pharmacodynamics assessments include CH₅₀, sheep red blood cell (sRBC), Wieslab enzyme-linked immunosorbent assay (ELISA), and C5. Blood samples for the pharmacodynamic (PD) assessments occur at each study visit (except the screening visit).

For subjects who have a dose increase to 0.3 mg/kg, samples for PD should be collected at pre-dose Day 1 of the new dose.

2.2.7 Pharmacokinetic Assessments

Blood samples for the measurement of plasma concentrations of RA101495 and metabolites will be collected on all subjects. All subjects will also have a blood sample for measurement of eculizumab plasma concentrations.

2.2.8 Schedule of Assessments

The following is the time and events table

Table 2: Time and Events Table

Phase	Screening Period	Treatment Period								
		0	1	2	3	4	6	8	10	12 (End of Study)
Study Week →	-8 to 1	0	1	2	3	4	6	8	10	12 (End of Study)
Study Day ^a →	-56 to -1	1 ± 2 ^b	8 ± 2	15 ± 2	22 ± 2	29 ± 2	43 ± 4	57 ± 4	71 ± 4	84 ± 4
Study Procedure ↓										
ICF process and signed ICF	X									
Review eligibility criteria	X	X								
Medical history and demographics	X									
Prior and concomitant medications	X	X	X	X	X	X	X	X	X	X
Physical examination	X	X				X				X
Height and weight ^c	X	X				X				X
Vital signs	X	X				X				X
Electrocardiogram	X	X				X				X
Neisseria throat swab ^d	X									
Neisseria vaccination ^d		X								
Ciprofloxacin treatment ^d		X	X	D14						
Blood chemistry ^e	X	X	X	X	X	X	X	X	X	X
Hematology	X	X	X	X	X	X	X	X	X	X
Coagulation ^f	X	X	X	X	X	X	X	X	X	X
Urinalysis	X	X	X	X	X	X	X	X	X	X
PNH clone size	X					X		X		X

Phase	Screening Period	Treatment Period								
		0	1	2	3	4	6	8	10	12 (End of Study)
Study Week →	-8 to 1									
Study Day ^a →	-56 to -1	1 ± 2 ^b	8 ± 2	15 ± 2	22 ± 2	29 ± 2	43 ± 4	57 ± 4	71 ± 4	84 ± 4
Pregnancy test ^a	X	X				X		X		X
Adverse events		X	X	X	X	X	X	X	X	X
Assessment of injection site reactions ^b		X	X	X	X	X	X	X	X	X
Pharmacokinetics RA101495 ^c		X	X	X	X	X	X	X	X	X
Pharmacokinetics eculizumab ^d	X	X		X		X	X			
Pharmacodynamics RA101495 ^e		X	X	X	X	X	X	X	X	X
Anti-drug antibody ^f		X ^g				X		X		X
Quality of life questionnaires										
EORTC-QLQ-C30		X				X		X		X
FACIT-Fatigue		X				X		X		X
EQ-5D		X				X		X		X
Treatment satisfaction assessment										X
Additional biomarker samples ⁱ		X	X	X	X	X	X	X	X	X
Pharmacogenomic analysis (optional) ^j		X ⁱ								
Electronic diary training, dispensation, and collection		X								X
RA101495 administration ^m		X	X	X	X	X	X	X	X	X
Study drug dispensing and return ⁿ		X	X	X	X	X	X	X	X	X

Abbreviations: EORTC-QLQ-C30=European Organization for Research and Treatment of Cancer-Quality of Life Questionnaire; EQ-5D=EuroQol 5D questionnaire; FACIT-F=Functional Assessment of Chronic Illness Therapy-Fatigue Scale; ICF=informed consent form; LDH=lactate dehydrogenase; NA=not applicable; PD=pharmacodynamic; PK=pharmacokinetic.

- a. Study Visits have a Visit window of ± 2 days after the actual planned Visit day for the first 4 weeks, and ± 4 days from week 6 to week 12.
- b. The Day 1 Visit should be scheduled to coincide with the next scheduled dose of eculizumab (i.e. 14 ± 2 after from the last eculizumab dose). Eculizumab should NOT be administered at the Day 1 Visit or at any time thereafter during the study.
- c. Height will be measured only at the Screening Visit.
- d. All subjects must have a negative throat swab for *Neisseria meningitidis* colonization for eligibility. All subjects must have documentation of prior *Neisseria meningitidis* vaccination (and booster if appropriate) prior to study entry.
- e. Including LDH for primary efficacy endpoint
- f. Coagulation tests should be performed, according to standard practice, on all subjects taking anticoagulant therapy.
- g. For all female subjects of childbearing potential, a negative serum pregnancy test must be documented at the Screening Visit and a negative urine pregnancy test must be documented at the Day 1 Visit prior to dosing. All other pregnancy tests will be urine.
- h. The injection site should be assessed at each clinic visit through Day 84 (End of Study).
- i. Blood samples for PK and PD and additional biomarker sampling at the following time points in relationship to the first dose of RA101495: pre-dose (within 1 hour before first dose administration) and at 1, 3, and 6 hours post-dose on Day 1. For subjects who have a dose increase to 0.3 mg/kg, samples for PK and PD should be collected at pre-dose Day 1 of the new dose, see footnote j. On clinic visit days PK and PD should be collected prior to administration of RA101495.
- j. Blood samples for PK of eculizumab should be collected at screening, Day 1, Day 15, Day 29, and Day 43 (2-week, 4-week, and 6-week) Visits. The sample should be collected prior to administration of RA101495.
- k. Blood sample for ADA on Day 1 must be obtained prior to dosing of RA101495.
- l. Blood sample for optional pharmacogenomic testing must be obtained on Day 1.
- m. On clinic visit days, the study drug RA101495 should be administered after blood samples for PK and PD are collected.
- n. Prefilled syringes containing RA101495 will be dispensed every 2 weeks. Subjects will also receive a secure container to dispose of used syringes at each visit and should bring the used container containing all used syringes to each study visit. All study drug (syringes) and disposal containers must be returned to the site at the last study visit. Dosing on study visit days will be held until the completion of the PK and PD sample blood collection has been completed.

3 STATISTICAL METHODS

3.1 General Methods

3.1.1 Computing Environment

All statistical analyses will be performed using SAS® Version 9.1.3 or higher for Windows.

3.1.2 Reporting of Numerical Values

All clinical study data will be presented in patient data listings. Descriptive statistics (n, mean, standard deviation, median, minimum, and maximum) will be calculated by treatment group for continuous variables. Confidence intervals will be provided where appropriate. For continuous endpoints, the confidence interval for the mean will be based on the t-distribution (e.g., CLM in the SAS Proc Means procedure).

Frequencies and percentages will be presented by treatment group for categorical and ordinal variables. If there are missing values, the number of missing values will be presented, but without a percentage and the number of non-missing values used as the denominator.

Means, medians, standard deviations, and confidence intervals will be reported to one decimal place more than the data reported on the CRF or by the laboratory/vendor. Minimum and maximum will be reported to the same number of decimal places displayed on the CRF or by the laboratory/vendor. P-values will be reported to 4 decimal places.

3.1.3 Baseline Value and Change from Baseline (if applicable)

Baseline value is defined as the most recent non-missing value obtained immediately prior to administration of first dose (i.e., generally the study day 1 assessment which occurs pre-dose).

Change from baseline will be calculated by subtracting the baseline value from the post-dose assessment for each patient (i.e. post-dose – baseline). Percent change from baseline will be calculated as $100 \times \text{change score} / \text{baseline score}$.

3.1.4 Handling of Missing/Incomplete Values

Unless otherwise explicitly specified, missing data will not be imputed; observed cases will be used in the analyses.

3.2 Analysis Populations

Analysis populations in this study are defined in the sections that follow.

3.2.1 Safety Population

The Safety Population will include all subjects who receive at least one injection of RA101495.

3.2.2 Efficacy Evaluable Population

The Efficacy Evaluable Population will include all subjects in the Safety Population who complete the 12-week Treatment Period.

3.2.3 Per Protocol Population

The Per Protocol Population will include all subjects in the Safety Population who complete the 12-week Treatment Period and have no major protocol violations.

Protocol violations will be assessed as “minor” or “major” during data review meetings that will take place prior to database lock.

3.2.4 Pharmacokinetic Population

The PK Population will include all subjects in the Safety Population who have at least 1 plasma sample obtained for PK assessment.

3.2.5 Pharmacodynamic Population

The PD Population will include all subjects in the Safety Population who have at least 1 plasma sample obtained for PD assessment.

3.3 Analysis Endpoints

3.3.1 Safety Endpoints

Safety assessments will include evaluation of AEs and SAEs (including major adverse vascular event (MAVE criteria), clinical laboratory tests, ECGs, vital signs, and physical examinations. Safety evaluation will also include a determination of anti-drug antibodies (ADA). Laboratory assessments will include PNH clone size.

3.3.1.1 Injection Site Reactions

The investigator will assess the injection sites at each scheduled visit for:

- Pain, tenderness, erythema, and induration severity (Table 3)
- Erythema and induration: maximum linear diameter
- Blisters, ulceration, necrosis: maximum linear diameter and severity

- Lymphadenopathy (absent, mild, moderate, or severe)

Table 3: Grading the Severity of Local Injection Site Reactions

Local Reaction to Injectable Product	Grade 1 (Mild)	Grade 2 (Moderate)	Grade 3 (Severe)	Grade 4 (Potentially Life Threatening)
Pain	Does not interfere with activity	Repeated use of non-narcotic pain reliever >24 hours or interferes with activity	Any use of narcotic pain reliever or prevents daily activity	Emergency room visit or hospitalization
Tenderness	Mild discomfort to touch	Discomfort with movement	Significant discomfort at rest	Emergency room visit or hospitalization
Erythema/redness	2.5 to 5.0 cm	5.1 to 10.0 cm	>10.0 cm	Necrosis or exfoliative dermatitis
Induration/swelling	2.5 to 5.0 cm and does not interfere with activity	5.1 to 10.0 cm or interferes with activity	>10.0 cm or prevents daily activity	Necrosis

3.3.2 Primary Efficacy Endpoint

The primary evaluation period is from Week 6 to Week 12. The primary efficacy endpoint is the change from baseline in serum LDH levels during this period, defined as the mean of the non-missing LDH values of Weeks 6, 8, 10, and 12 minus the baseline LDH value (defined in Section 3.1.3).

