10.1.2.1 DOSE ESCALATION

After 2 weeks of treatment with RA101495 at 0.1 mg/kg, if a subject has not achieved an adequate response (defined as an LDH <1.5xULN), the dose should be escalated to 0.3 mg/kg daily. Dose escalation may proceed only if no severe (i.e. Grade ≥3) or serious treatment-emergent adverse events are reported at the 0.1 mg/kg dose.

For subjects who have a dose increase to 0.3 mg/kg, samples for PK and PD should be collected at pre-dose of the first day of the new dose, then at scheduled visits per the Time and Events Table (Table 1).

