12.1.3.6 DOSE MODIFICATION FOR OTHER ADVERSE EVENTS

For all Grade ≥ 3 treatment-emergent AEs (other than the hepatic and pancreatic AEs described in [sections 12.1.3.2](#) and [12.1.3.3](#)), study drug should be dose-reduced (if at the 0.3 mg/kg daily dose) or permanently discontinued (if at the 0.1 mg/kg daily dose).

All AEs should be recorded as AEs per [Section 12.1](#) and [Section 12.3](#).

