3.9.2 Secondary Efficacy Endpoints Analysis

Secondary efficacy endpoints include the change from baseline values at each of the following scheduled post-baseline assessment time-points:

- total hemoglobin,
- free hemoglobin,
- haptoglobin,
- reticulocytes
- hemoglobinuria (note: hemoglobinuria will be assessed using a urine colorimetric scoring system).

The change from baseline for each of these endpoints will be assessed by a two-sided Wilcoxon signed-rank test. Additionally, the summary statistics will be presented for the values, change, and percent change from baseline scores.

Additionally, the secondary endpoint of an LDH score $< 1.5 \times \text{ULN}$ (i.e., a dichotomous endpoint) will be assessed at the primary evaluation period and the scheduled post-baseline assessment time-points by means of a one-sided exact McNemar's test.

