3.12 Replacement of Subjects

Enrolled subjects who prematurely discontinue study treatment for any reason prior to the Day 84 Visit may be replaced, at the discretion of the Sponsor.

4 References

EuroQol Group. EuroQol-a new facility for the measurement of health-related quality of life. *Health Policy* 1990; 16:199-208.

5 List of Tables, Figures, and Listings

Table shells will be provided in a separate document.

Table Number	Table Title
14.1.1	Patient Disposition
14.1.2.1	Medical History; Safety Population
14.1.2.2	PNH Disease History; Safety Population
14.1.2.3	PNH Treatment History; Safety Population
14.1.3.1	Prior Medications; Safety Population
14.1.3.2	Concomitant Medications; Safety Population
14.1.4	Exposure to Study Treatment; Safety Population
14.1.5.1	Demographics; Safety Population
14.1.5.2	Demographics; Efficacy Evaluable Population
14.1.5.3	Demographics; Per Protocol Population
14.1.5.4	Demographics; Pharmacodynamic Population
14.2.1.1	Summary of LDH Values; Safety Population
14.2.1.2	Summary of LDH Values; Efficacy Evaluable Population
14.2.1.3	Summary of LDH Values; Per Protocol Population
14.2.1.4	Summary of LDH Values; Pharmacodynamic Population
14.2.2.1	Summary of Total Hemoglobin Values; Safety Population
14.2.2.2	Summary of Total Hemoglobin Values; Efficacy Evaluable Population
14.2.2.3	Summary of Total Hemoglobin Values; Per Protocol Population
14.2.2.4	Summary of Total Hemoglobin Values; Pharmacodynamic Population
14.2.3.1	Summary of Free Hemoglobin Values; Safety Population
14.2.3.2	Summary of Free Hemoglobin Values; Efficacy Evaluable Population
14.2.3.3	Summary of Free Hemoglobin Values; Per Protocol Population

Table Number	Table Title

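### Under the supplied SAP text, a subject who stops drug before Week 6 normally drops out of the primary-period LDH change and the primary-period LDH <1.5×ULN rate, and may be replaced

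*SAP*

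**What the plan says.** - **Primary endpoint.** SAP 3.3.2, repeated in 3.9.1, takes the LDH change as "defined as the mean of the non-missing LDH values of Weeks 6, 8, 10, and 12 minus the baseline LDH value". No rule covers a subject with none of the four values.
- **Missing data.** SAP 3.1.4 sets the default: "missing data will not be imputed; observed cases will be used in the analyses". The efficacy sections make no exception.
- **Percentages.** For categorical results, SAP 3.1.2 says "the number of missing values will be presented, but without a percentage and the number of non-missing values used as the denominator".
- **LDH <1.5×ULN.** Under SAP 3.9.2 this secondary endpoint "will be assessed at the primary evaluation period and the scheduled post-baseline assessment time-points", with a one-sided exact McNemar test.
- **Populations.** The Efficacy Evaluable Population is "all subjects in the Safety Population who complete the 12-week Treatment Period" (SAP 3.2.2), and the Per Protocol Population also requires completion. SAP section 5 plans LDH summaries for the Safety, Efficacy Evaluable, Per Protocol and Pharmacodynamic Populations (Tables 14.2.1.1 to 14.2.1.4). SAP 3.9.1 does not name the population for the primary test.
- **After stopping.** Protocol 8.4.1 asks for one End-of-Study Visit, with clinical chemistry (LDH is in that panel, Table 4). It schedules nothing further.
- **Replacement.** SAP 3.12: "Enrolled subjects who prematurely discontinue study treatment for any reason prior to the Day 84 Visit may be replaced", at the sponsor's discretion. Protocol 9.3.2 says this is to secure enough evaluable subjects.

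**The concern.** The primary evaluation period opens at the Week 6 visit (Day 43 ± 4). A subject off drug before then normally has nothing for the primary endpoint to average. The Safety Population table does not rescue the case, because it follows the same observed-case rule.

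This applies whatever the reason for stopping. It matters when the reason is tied to the outcome. One such route is a Grade 3 or higher hemolysis event at 0.1 mg/kg: Protocol 12.1.3.6 makes that a permanent stop, and 10.1.2.1 bars escalation after it. For a subject who is never controlled, the route runs mainly in about the first two weeks, before escalation to 0.3 mg/kg applies. Later it needs a breakthrough after control, or a second event after dose reduction.

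In that case a failure leaves the two primary-period results, and a replacement restores the sample size without restoring the failure. With 6 to 8 subjects, one person is 12.5% to 16.7% of the trial.

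**Working it through.** **Inputs.** SD 443 U/L at baseline and post-baseline, correlation 0.8, n = 6, stated standard error about 114 U/L (SAP 3.11, Protocol 13.1). The number of early stoppers and their LDH are not in the documents. I assume one stopper whose change is D worse than the mean of the others, with D equal to 1 to 2 SD of the change.

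**1. Reproduce the plan's figure.** SD of change = 443 × √(2 × (1 − 0.8)) = 280.2 U/L. Standard error at n = 6 is 280.2/√6 = 114.4 U/L, which matches the stated 114. So D runs from 280.2 to 560.4 U/L.

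**2. Trace the subject through the outputs.**

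| Output | Early stopper counted? |
|---|---|
| Week 6–12 LDH change, all four populations | Normally no |
| LDH <1.5×ULN, primary period | Normally no; outside the denominator |
| LDH and LDH <1.5×ULN at Week 1–4 visits attended | Yes (not in the completer populations) |
| Listings, missing count, discontinuation summaries | Yes |

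**3. Shift in the mean change.** If the others average M and the omitted subject has M + D, the mean over all N treated is M + D/N, while the observed-case mean is M. The flattering shift is therefore D/N.

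| Case | D = 280.2 | D = 560.4 | In planned SEs |
|---|---|---|---|
| 6 treated, 5 analysed | 46.7 U/L | 93.4 U/L | 0.41 to 0.82 |
| 7 treated, 6 analysed (replaced) | 40.0 U/L | 80.1 U/L | 0.35 to 0.70 |

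**4. Primary-period LDH <1.5×ULN rate if all others respond** (exact 95% intervals).

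| Case | Observed cases | All treated |
|---|---|---|
| No replacement | 5/5 = 100% (47.8 to 100) | 5/6 = 83.3% (35.9 to 99.6) |
| One replacement | 6/6 = 100% (54.1 to 100) | 6/7 = 85.7% (42.1 to 99.6) |

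**5. McNemar p-value.** If the omitted subject was at or above 1.5×ULN at baseline, counting a failure adds a concordant pair, which the test ignores. Five conversions give 0.5⁵ = 0.031 either way, and six give 0.5⁶ = 0.016. The loss then shows in the proportion, not the p-value.

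**The case against.** **The operative SAP may differ.** The post-lock amendment builds on SAP Version 3.0 of 22 March 2018. The supplied SAP body cites protocol version 1.1 of October 2016, while the supplied protocol is Amendment 1 of January 2017. The amendment's output list keeps the four LDH tables, but table titles say nothing about missing-data rules. This stands: a reader might infer that the final analysis used these rules, and the documents do not show that.

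**The subject is not hidden.** A reader might infer that the failure vanishes from the report, or from the LDH <1.5×ULN analysis altogether. It does not: step 2 shows where it stays, and a 5/5 would carry a missing count of one. This confines the effect to the two primary-period results.

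**The exclusion is not absolute.** An early End-of-Study LDH could fall within Day 43 ± 4. Both schedules also label Week 12 as End of Study, and the SAP has no mapping rule. This stands, and is why the claim says normally.

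**The outcome-linked route is assumed.** Inadequate response leads to escalation ("After 2 weeks of treatment with RA101495 at 0.1 mg/kg, if a subject has not achieved an adequate response"), and lack of efficacy is not a listed withdrawal reason in Protocol 9.3.1. Severity criteria sit in a separate manual, so the documents do not show what grade uncontrolled hemolysis would receive. Some early stops, such as those for raised amylase or lipase, have no stated link to LDH. All of this stands, and the size is therefore conditional.

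**The stopping rule.** A reader might infer that permanent discontinuation at 0.1 mg/kg is the fault. It is a defensible safety choice. The fault lies only in how the stopped subject is then counted.

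**Conclusion.** The point holds on the supplied text, at minor severity. The plan's own rules, rather than a gap in them, normally remove a subject who stops before Week 6 from the primary-period LDH change and from the primary-period LDH <1.5×ULN denominator, and they allow replacement.

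If the stop reflects poor hemolysis control, both results are flattered. For one subject 1 to 2 SD worse than the others, the shift is 40 to 93 U/L, under one planned standard error. If all others respond, 5/5 stands in place of 5/6, or 6/6 in place of 6/7. These sizes rest on one assumed stopper, an assumed deficit, and the plan's SD and correlation.

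A reader might go further and infer that the primary signed-rank result would be overturned. If the other subjects' LDH all fell and the omitted subject were scored as the largest increase, the two-sided exact p-value would move from 0.0625 (five analysed) to 0.4375 (six), or with replacement from 0.031 (six) to 0.297 (seven). That requires a rise larger than every other subject's fall, which nothing in the documents supports. It is an upper extreme, not an estimate.

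**What to change.** Leave the stopping rule as it is and make two additions.

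1. **SAP 3.9.2.** Beside the observed-case rate, report the primary-period LDH <1.5×ULN rate with all treated subjects as denominator, including those later replaced. Count a subject with no on-treatment LDH in Weeks 6–12 as not achieving it. This departs from the non-missing denominator of 3.1.2 for this one result.
2. **SAP 3.9.1, Table 14.2.1.1 (Safety Population).** Add one sensitivity row in which a subject with no Week 6–12 value contributes the early End-of-Study LDH, or the last LDH before eculizumab if that was restarted first. State that an early End-of-Study record is not mapped to Week 12.

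The amendment shows that the database is locked. Both should therefore be reported as labelled post hoc analyses, as SAP section 1 requires, unless Version 3.0 already specifies them.

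**Cost.** A few sentences of text, one extra rate and one table row. The LDH is already drawn at the early End-of-Study Visit, so no visits or patients are added.

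**Downsides.** The first addition counts safety stops unrelated to hemolysis as failures. In the second, a single early LDH may overstate failure if drawn in an acute episode, or understate it while residual eculizumab remains (the protocol samples eculizumab up to Day 43). Showing the observed-case result alongside lets the reader judge both.
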